Aim 2: To evaluate the effect of 6 weeks of creatine supplementation on ³¹P-MRS neuroimaging data among persons with MDD. We hypothesize that creatine supplementation of persons with MDD receiving ECT will promote increases in frontal cortical concentrations of phosphocreatine (and phosphocreatine to total phosphorus ratios) relative to baseline, while placebo supplementation will have no impact on phosphocreatine levels.

Aim 3: To determine if creatine supplementation throughout an ECT course leads to decreased cognitive adverse effects of ECT as measured by changes in the Montreal Cognitive Assessment (MoCA) score, compared to placebo. We hypothesize that creatine augmentation during ECT therapy will be protective against cognitive adverse effects, as measured by changes in subjects' MoCA scores between baseline and 8 weeks, when compared to placebo.

IV. Methods

A. Eligibility Criteria

Participants with a diagnosis of Major Depressive Disorder with moderate to severe symptoms will be randomly assigned in a 1:1 ratio to either ECT with creatine augmentation or ECT with placebo augmentation or 6 weeks. Individuals must meet criteria for major depressive episode for a duration of at least 2 months in order to participate. Participants must be greater than 18 years of age and considered to be a good candidate for ECT based on clinical assessment. Individuals who are pregnant or breast-feeding or who possess any other contraindication to ECT will not be invited to participate. Participants can receive ECT treatments in either inpatient or outpatient setting at the University Neuropsychiatric Institute.

Individuals who meet diagnostic criteria for other psychiatric conditions apart from major depressive disorder (including Bipolar I, Bipolar II, or personality disorders) will not be invited to participate. Individuals with substance use disorders will be excluded because substance use disorders typically confound the diagnosis of depression and can contribute to treatment resistance. Individuals will not be considered for study participation if they have *renal disease* because to date it cannot definitively be stated if short and long-term creatine usage is or is not harmful to the kidneys. Appropriate renal function will be determined based on normal creatinine clearance, determined by routine laboratory work (basic metabolic panel).

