Participants will be recruited from a population of patients who have already been referred for ECT and who have had initial clinical assessments to determine whether ECT is indicated. As this study is an add-on to standard clinical care only, routine ECT procedures will be followed, though the ECT service (attending psychiatrist, anesthesiologist) will be notified of subject participation. In general, subjects will, after being medically cleared for ECT (psychiatric exam, physical exam, EKG, laboratory studies if indicated), received bifrontal ECT every other day for between 6 and up to roughly 14 treatments, with a total duration of treatment lasting between two and four weeks. Anesthesia for ECT is provided by a board-certified anesthesiologist and comprises the use of methohexital, midazolam, etomidate, or ketamine, as indicated, and at the discretion of the anesthesiologist. Participants may receive interventions designed to augment the likelihood of a seizure being achieved, such as a caffeine infusion, hyperventilation, or other techniques, at the discretion of the treating ECT psychiatrist and anesthesiologist. After ECT, participants are monitored for recurrent seizure/status epilepticus and for vital sign abnormalities for roughly thirty minutes, then released to home (if outpatient) with 24 hour per day supervision by adult family members, or else escorted back to the inpatient unit, where they again receive 24 hour per day supervision by unit staff. Prior to each treatment, subjects complete a Quick Inventory of Depressive Symptoms (QIDS) to assess their overall burden of depressive symptoms. The exact duration of treatment/number of treatments is determined by the treating ECT psychiatrist, based on clinical response. The study will record all pertinent variables related to ECT as noted in the clinical record, including number of treatments, QIDS score, number of seizures per treatment session, seizure duration, adverse effects, augmentation strategies, anesthesia type, and vitals.

2. Drug Dosing

Participants who have been assigned to the creatine arm of the trial will receive a 20g loading dose daily for 1 week starting as soon as possible before ECT begins and after completion of the

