MRI scans will be conducted twice: after the baseline visit and prior to initiating ECT, and following completion of the ECT series (i.e., after ~3 weeks, and during the 2 week post-ECT follow-up period). The 3.0 Tesla Siemens Prisma whole-body clinical scanner (Siemens Medical Solutions. Erlangen, Germany) located within the University Neuropsychiatric Institute (UNI) will be used to acquire this data. Participants will first undergo a routine anatomic MRI protocol, which includes MRI images acquired in the axial and coronal planes. Specifically, the anatomic scan protocol consists of a T1 weighted structural scan (MP2RAGE), and double-echo T2 weighted scan, and a Fluid Attenuated Inversion Recovery scan (FLAIR). The purposes of the MR anatomic screening session include screening subjects for gross structural abnormalities and acquiring images for use in brain cortical thickness measurements. Anatomic MRI examinations will be performed with Siemens 64 channel head coil. After localization, anatomical imaging will be obtained using a T1weighted, sagittal oriented 3D-Magnetization Prepared Rapid Gradient Echo (MPRAGE) sequence (TR/TE/TI 5000/2.93/700 ms, matrix 256x256, FOV 256x256 mm, flip angle 4 degree, slice thickness 1.0 mm, slab 176 mm, bandwidth 240 Hz/pixel). Axial proton-density and T2 weighted images will be acquired to screen for brain structural abnormalities using 2D Double echo T2 weighted turbo spin echo (TSE) sequence (TR 7110 ms, TE 28/84 ms, FOV 240x210, slice thickness 3 mm, flip 150°, bandwidth 179 Hz/pixel). FLAIR sequence (TR/TE/TI 8000/90/2500 ms, slice thickness 5 mm, FOV 240x168, voxel size 0.8x0.6x5.0 mm, bandwidth 200 Hz/pixel, turbo factor 13) will be used to detect juxtacortical-cortical lesions. All anatomic MRI images will be read by a board-certified, CAQ neuroradiologist to screen for structural abnormalities.

b. Measurement of *In-Vivo* Brain Chemistry Using Phosphorus-31 Magnetic Resonance Spectroscopy (³¹P-MRS)

Phosphorus spectroscopy data will be acquired on the same Siemens 3T system. We aim to keep

the duration of each MRSI examination at or under 25 minutes. A 3D-MRSI sequence with elliptically weighted phase-encoding will be used to collect ³¹P-MRSI data to minimize T2 signal decay. Acquisition parameters will be: data matrix size 16x16x8; TR 2000 ms; tip-angle 90 degree for hard RF pulse; Rx bandwidth ±1 kHz; complex-points 1024; readout duration 256 ms; pre-acquisition delay 0.3ms; FOV 240x240 mm²; 16 NEX.

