Aim 1: To evaluate the effect of creatine supplementation on response to ECT over the course of 6 weeks among persons with MDD.

As this is a pilot study, we have limited information regarding the potential magnitude of the effect of creatine supplementation on HAM-D scores in patients receiving ECT. Based on a prior recommendation that one assume a minimum detectable score of 7 for the HAM-D in randomized control trials, with a moderate effect size of 0.875 [72], we estimate that a sample size of 30 depressed subjects (15 active vs. 15 placebo) will have ~82% power to detect a significant difference between groups using a linear mixed model with first-order autoregressive covariance structure.

Aim 2: Aim 2: To evaluate the effect of 6 weeks of creatine supplementation on ³¹P-MRS neuroimaging data among persons with MDD.

Following 8 weeks of oral creatine, adult female methamphetamine users had significantly increased PCr levels [73]. The standardized effect size was 0.920. Also, a study involving openlabel creatine supplementation in depressed adolescents demonstrated significantly increased PCr levels following creatine administration [68]. The change of PCr levels was approximately 6.2% of the mean with 9.6% SD. Therefore, if we set the anticipated minimum detectable effect size (MDES) = 9% with SD = 10% for this project, a total sample size of 30 (15 active vs. 15 placebo) would have ~80% power to detect the anticipated effect using a repeated measures design.

VI. Administrative Procedures

A. Study Drug Administration

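### Aim 2's stated power of about 80% does not follow from its inputs: on the natural reading, 15 per arm with a 9% difference and SD 10% gives about 66%

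*Combined protocol and SAP*

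**What the plan says.** Section V (Statistical Plan and Sample Size Determination), Aim 2, cites two earlier results. For women using methamphetamine: "The standardized effect size was 0.920". For depressed adolescents: "The change of PCr levels was approximately 6.2% of the mean with 9.6% SD". From these it concludes that if the investigators "set the anticipated minimum detectable effect size (MDES) = 9% with SD = 10% for this project, a total sample size of 30", with 15 in each arm, the trial "would have ~80% power to detect the anticipated effect using a repeated measures design".

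That is all the statistical detail for Aim 2. There is no alpha, sidedness, named test or contrast, no statement of whether the 10% is the SD of a change or of a single measurement, and no correlation between scans. Aim 1, in the same section, at least names its model: "using a linear mixed model with first-order autoregressive covariance structure".

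Three other places bear on the reading:

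- IV.C.4, Imaging: "MRI scans will be conducted twice: after the baseline visit and prior to initiating ECT, and following completion of the ECT series". There is one baseline value and one follow-up value.
- IV.C, Drug Dosing: the loading dose is given "starting as soon as possible before ECT begins and after completion of the" phosphorus scan, so scan 1 precedes treatment.
- III, Specific Aims, Aim 2: PCr is expected to rise under creatine "relative to baseline, while placebo supplementation will have no impact on phosphocreatine levels".

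**The concern.** With one pre-treatment and one post-treatment scan, the arm-by-time test in a repeated-measures model is the same as a two-sample t test on change. The repeated-measures label therefore adds no power if the 10% is already the SD of change. That is how the sentence reads: the 10% follows directly from an SD of 9.6% attached to a change in PCr. A standardised difference of 0.90 with 15 per arm falls well short of 80% at two-sided 5%.

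Aim 2 is the trial's test of whether creatine raises brain PCr. A null result set against a stated 80% power would look like stronger evidence against a PCr effect than it is. As the plan stands, nobody can check the figure, because the inputs needed to reproduce it are absent.

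**Working it through.** **Inputs from the plan.** n = 15 per arm; difference 9%; SD 10%; two scans; cited effects 0.920 and 6.2/9.6 = 0.646.

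**Assumptions, because the plan is silent.** Two-sided 5%; all 30 participants have both scans; SD 10% is the SD of change unless stated otherwise; scan-to-scan correlation ρ between 0.3 and 0.7; equal variance at the two scans.

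**1. Trying to reproduce 80%: between-arm t test on change.** The noncentrality is d × √(n/2), with d = 9/10 = 0.90, so 0.90 × √7.5 = 2.465. The critical value on 28 df is 2.048. Power from the noncentral t is 66.3%. The normal approximation, Φ(2.465 − 1.960), gives 69.3%. Neither is about 80%.

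| Effect | d | Noncentrality | Power |
|---|---|---|---|
| 9% / 10% (planned) | 0.900 | 2.465 | 66% |
| cited standardised effect | 0.920 | 2.520 | 68% |
| 6.2% / 9.6% (cited change) | 0.646 | 1.769 | 40% |

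Power of 80% needs d = 1.060, a difference of 10.6% at SD 10%.

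**2. Readings that do give about 80% at 9%.** Each needs an input that the plan does not state.

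- One-sided 5%: 77.6% (t), 79.4% (normal approximation).
- SD 10% as a single-scan SD, change score: SD of change = 10√(2(1 − ρ)). Power is 52 / 66 / 87% at ρ = 0.3 / 0.5 / 0.7, and 80% at ρ ≈ 0.64.
- SD 10% as a single-scan SD, ANCOVA: residual SD = 10√(1 − ρ²). Power is 69 / 77 / 90% at ρ = 0.3 / 0.5 / 0.7, and 80% at ρ ≈ 0.55.
- SD 10% as the SD of change, ANCOVA: see step 4; 80% needs ρ of about 0.39 or lower.

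**3. Readings that do not support the figure.**

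- Paired test within the creatine arm: 0.90 × √15 = 3.486 on 14 df gives 90% (64% at 6.2%/9.6%). It does not compare the arms.
- Between-arm test on the mean of both scans, ρ = 0.5, single-scan SD 10%: SD of the mean = 10√0.75 = 8.66. Power is 78% only if the 9% difference is present at both scans. Scan 1 precedes dosing, so the difference in means is 4.5%, and power is 28%.

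**4. ANCOVA with SD of change 10%.** Residual SD = SD of change × √((1 + ρ)/2), 27 df, averaged over chance baseline imbalance (variance of the estimated difference multiplied by 1 + F/28, with F ~ F(1, 28)). A simulation of 100,000 trials per cell agreed to within 0.3 percentage points.

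| ρ | Residual SD at 10% | Power, 9%/10% | Power, 6.2%/9.6% | Difference for 80% (SD 10%) |
|---|---|---|---|---|
| 0.3 | 8.06 | 82% | 55% | 8.7% |
| 0.5 | 8.66 | 77% | 49% | 9.4% |
| 0.7 | 9.22 | 72% | 44% | 10.0% |

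**5. Taking the 80% as given.** Suppose some two-sided reading does yield 80% at 9%/10%, and 9.6% plays the same role as 10%. A noncentrality of 2.902 gives 80% on 28 df. Scaling it by 0.646/0.90 gives 52% at the cited adolescent change; scaling by 0.920/0.90 gives 82%. The planned 0.90 thus sits near the top of the two cited effects.

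**The case against.** The strongest reply is that no sum has been shown to be wrong. The plan omits its assumptions, and several reasonable ones lead to about 80%. The Aim 2 hypothesis is directional, which gives a one-sided test some support. The SD attached to the adolescent change could be a spread of levels, and only the cited study could settle that. ANCOVA, the analysis recommended here, gives 77% to 82% for correlations of 0.5 down to 0.3, which is close to the stated figure. The plan also never claims 80% power at 6.2%, and this is a pilot whose imaging result would be judged mainly from its confidence interval.

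Much of this stands. The figure is not proven wrong, the SD type is an inference, and the 6.2% results show sensitivity to the effect size; they do not contradict the plan's claim. But a directional hypothesis does not specify a one-sided test, and no section names ANCOVA or gives a correlation. The routes to 80% rest on different assumptions, and the plan adopts none of them. Being a pilot does not excuse a power figure that cannot be checked, since the plan chose to state one.

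**Conclusion.** The concern holds. The stated power of about 80% is unsupported as written. On the natural reading (between-arm comparison of change, two-sided 5%, SD 10% as the SD of change, complete data) it is about 66%, so a true 9% difference would be missed about 34% of the time instead of 20%. For a difference the size of the cited adolescent change, the miss rate is about 60% with the change score, and 45% to 56% with ANCOVA over the assumed correlations.

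Confidence is moderate, because the result depends on the sidedness and on what the 10% SD measures, and the plan states neither. Missing scans would lower power further: the change-score figure falls to 63% with 14 per arm and 56% with 12. Section IV.B foresees withdrawals, and the sample size makes no allowance for them. This should be fixed before the imaging result is interpreted.

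**What to change.** 1. Name the Aim 2 test as the creatine-versus-placebo difference in post-ECT PCr adjusted for baseline PCr (ANCOVA), with a 95% confidence interval, and word the hypothesis as that between-arm contrast. Scan 1 already supplies the baseline value.
2. Replace the 80% statement with the power of the named test. State alpha, sidedness, whether the 10% is the SD of a change or of a single scan, and the assumed correlation. Suggested text for ANCOVA with SD of change, two-sided 5%: *about 72 / 77 / 82% at 9%/10% and 44 / 49 / 55% at 6.2%/9.6% for correlation 0.7 / 0.5 / 0.3; 80% power at a difference of about 10.0 / 9.4 / 8.7%*. If the change-score test is kept: *about 66% at 9%/10% and 40% at 6.2%/9.6%; 80% power at 10.6%*. If the 10% is a single-scan SD, say so and use the corresponding figures in step 2 of the working.
3. State that these figures assume both scans in all 30 participants.

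The cost is protocol and SAP wording, including naming an analysis that the plan leaves open. No participants, scans or visits are added. The only downside is a less favourable stated power on most of these readings.
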